2.0 LIST OF ABBREVIATIONS

AE	Adverse Event
antiHBs	Antibody to the hepatitis B surface antigen
CFR	Code of Federal Regulations
CRF	Case Report Form
CTCAE	Common Terminology Criteria for Adverse Events
DHHS	Department of Health and Human Services
DMC	Data Monitoring Committee
DSMB	Data & Safety Monitoring Board
DSMC	Data & Safety Monitoring Committee
DSMP	Data & Safety Monitoring Plan
eCRF	Electronic Case Report Forms
EDC	Electronic Data Capture
FDA	Food and Drug Administration
GCP	Good Clinical Practice
HepB-CpG	Hepatitis B vaccine with CpG adjuvant (Heplisav-B™)
HIPAA	Health Insurance Portability and Accountability Act
ICTR	Institute for Clinical and Translational Research
IND	Investigational New Drug Application
IRB	Institutional Review Board
MOP	Manual of Procedures
NCI	National Cancer Institute
NIH	National Institutes of Health
OHRP	Office for Human Research Protections
PHI	Protected Health Information
PI	Principal Investigator
POC	Point of Contact
PRC	Pharmaceutical Research Center
SAE	Serious Adverse Event
SAP	Statistical Analysis Plan
sIRB	single IRB
SMART IRB	Streamlined, Multisite, Accelerated Resources for Trials IRB
SMC	Safety Monitoring Committee
SMP	Study Monitoring Plan
SMS	Study Monitoring Service
UP	Unanticipated Problem

3.0 STUDY SUMMARY

3.1 Synopsis

Full Title	HepB-CpG series for healthcare workers who are hepatitis B vaccine nonresponders
Short Title	Vaccination for healthcare worker hepatitis B vaccine nonresponders
Protocol Number	[HS IRB 2020-0631]
ClinicalTrials.gov Identifier & Summary	
pending
 
This study is being done to determine if healthcare workers who have previously failed to respond to hepatitis B vaccine series will respond to a hepatitis B with CpG adjuvant (hepB-CpG) (Heplisav-B)

Number of Site(s)	The study will be conducted at UWHealth Employee Health Services
Phase	Phase 4
Main Inclusion Criteria	
Healthcare worker who has previously received at least 5 doses of hepatitis B vaccine with aluminum adjuvant (Recombivax B or Engerix B) and has an antibody to the hepatitis B surface antigen (antiHBs) that is less than 10 mIU/ml.English-speaking (able to provide consent)
Main Exclusion Criteria	
Allergy to hepB-CpG or a component
Objective(s)	
Primary Objective
 
To measure the number of healthcare workers who failed to respond to 5 or more doses of hepatitis B vaccine with aluminum adjuvant who will respond to hepatitis B vaccine with CpG adjuvant series. 
Secondary Objectives
 
To measure the number of healthcare workers who respond to a single dose of hepB-CpGTo determine risk factors associated with hepatitis B vaccine nonresponse, including age, smoking status, sex, diabetes, immunosuppression
Endpoints	
Primary Endpoint
 
AntiHBs >10 mIU/ml following two doses of hepB-CpG 
Secondary Endpoint
 
AntiHBs >10 mIU/ml following a single dose of hepB-CpGMeasure effect of known hepatitis B vaccine nonresponse risk factors on response in this population
Study Design	Open label
IND or IDE Number	Not applicable

Study Intervention	Each individual who has completed at least 5 doses hepB vaccine with aluminum adjuvant series but is anti-HBs negative will be contacted by EHS staff and invited to receive the hepB-CpG two dose series on a 0 and 1 month schedule. Antibody to the surface antigen will be measured after the first dose during the visit for the administration of the second dose. One month after completion of the series, each immunized individual will have another anti-HBs measured.
Total Number of Subjects	Up to 130 individuals will be recruited and enrolled.
Study Population	Healthcare workers who have received at least 5 doses of hepatitis B vaccine with aluminum adjuvant and have antiHBs < 10mIU/ml.
Statistical Methodology	We will count the number of individuals who seroconvert and have anti-HBs >10 mIU/ml and report a ratio with the total number immunized as the denominator. We will develop a multivariate model to predict hepB-CpG response which will include age, sex, smoking status, diabetes, and immunosuppression as variables.
Estimated Subject Duration	The duration of the study for each subject is approximately 8 weeks.
Estimated Enrollment Period & Study Duration	Study enrollment and follow-up will occur over 12 months.

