5.0 INTRODUCTION

5.1 Disease Background

Although the recombinant hepatitis B (hepB) vaccine with aluminum adjuvant as a three dose series induces seroprotection in about 95% of individuals, a small number of healthy individuals fail to mount an immune response. Increasing age is an important risk factor for hepB vaccine response.¹ Healthcare personnel are among the individuals for whom protection from hepatitis B infection is very important. Employee Health Service (EHS) at the University of Wisconsin Hospital and Clinics screens employees with documented history of completion of the hepB vaccine 3-dose series for antibody to the hepatitis B surface antigen (anti-HBs) at time of hire. Those who are found to have anti-HBs less than 10 mIU/ml receive a challenge dose.² If the anti-HBs remains less than 10 mIU/ml, two more doses of vaccine are administered. Among the 15,000 employees, about 100 individuals have completed two hepB vaccine with aluminum adjuvant series but remain vaccine non-responders. Heplisav-B (hepB-CpG) is a recently licensed hepB vaccine with a new adjuvant that is more immunogenic in the general adult population and patients with chronic kidney disease or diabetes.³⁻⁵ Given the superior immunogenicity of hepB-CpG in these individuals who were difficult to induce seroprotection, we hypothesize that 70% of the 101 non-responders will mount an immune response to two doses of hepB-CpG.

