7.2 End of Study Definition

A subject is considered to have completed the study if they receive both doses of hepB-CpG and the blood draw one month after the second dose.

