8.5 Early Termination and Withdrawal

Subjects are free to withdraw from participation in the study at any time upon request.

The Principal Investigator (PI) may discontinue or withdraw a subject from the study for the following reasons at her discretion:

- Pregnancy
- Subject non-compliance with study requirements (e.g., study intervention non-compliance)
- If any clinical adverse event (AE), laboratory abnormality, or other medical condition or situation occurs such that continued participation in the study would not be in the best interest of the subject
- If the subject is no longer an appropriate candidate for participation

The following actions must be taken if a subject withdraws, or fails to return for a required study visit:

- The site will attempt to contact the subject and reschedule the missed visit by email and phone as in 8.4 above and counsel the subject on the importance of maintaining the assigned visit schedule and ascertain if the subject wishes to and/or should continue in the study.

- Before a subject is deemed lost to follow-up, the investigator or designee will make every effort to regain contact with the subject as described in 8.4 above. These contact attempts shall be documented in the study file.
- If the subject continues to be unreachable, s/he will be considered to have withdrawn from the study with a primary reason of lost to follow-up. The withdrawn date is the last day of attempted contact.

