13.0 STUDY ANALYSIS

13.1 Statistical Hypotheses

- **Primary Efficacy Endpoint(s):**

AntiHBs >10 mIU/ml following two doses of hepB-CpG

Descriptive statistics will be used to report the result, including number of responders and ratio of responders.

- **Secondary Efficacy Endpoint(s):**

AntiHBs >10 mIU/ml following two doses of hepB-CpG

Descriptive statistics will be used to report the result, including number of responders and ratio of responders.

Proportion of participants who are nonresponders with each risk factor and develop a multivariate model

Descriptive statistics will be used to report the result for each risk factor, including number of responders and ratio of responders. Multivariate analysis will be used to develop a model.

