13.3 Subject Population(s) for Analysis

Analyses will include all individuals who received at least one dose of hepB-CpG. We will also do a per-protocol analysis for hepB-CpG one dose and two doses.

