13.4 Statistical Methods

Descriptive statistics will be used to report the number and ratio of vaccine responders to both doses and one dose and with regard to known risk factors for hepatitis B vaccine nonresponse. A multivariate model with the risk factors will be developed.

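### Does the five-factor response model need a named method and a missing-titre rule when only about 30 non-responders are expected?

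*Combined protocol and SAP*

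**What the plan says.** Identifying risk factors for non-response is a secondary objective (3.1 and 6.0). For the model, the synopsis says "We will develop a multivariate model to predict hepB-CpG response which will include age, sex, smoking status, diabetes, and immunosuppression as variables". Section 13.1 says "Multivariate analysis will be used to develop a model" and section 13.4 says "A multivariate model with the risk factors will be developed". Section 13.1 also plans descriptive counts and ratios of responders for each factor. No section names a regression type, a coding for age or smoking, or an approach to sparse data.

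The expected response is in section 5.1: "we hypothesize that 70% of the 101 non-responders will mount an immune response to two doses of hepB-CpG". The synopsis caps enrolment at 130, and section 16.2 estimates about 100 eligible people.

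On populations, section 13.3 begins "Analyses will include all individuals who received at least one dose of hepB-CpG". Its next sentence adds per-protocol analyses for one dose and for two doses, without defining membership or tying either to the model. Section 7.2 counts a subject as having completed the study "if they receive both doses of hepB-CpG and the blood draw one month after the second dose". For the response count, the synopsis will "report a ratio with the total number immunized as the denominator". The model sentence follows separately and sets no denominator.

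**The concern.** Two things look wrong.

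The first is sparseness. Five factors and about 30 non-responders give few events per coefficient. Ordinary logistic regression then tends to overstate odds ratios, and it can give infinite ones when everyone with an uncommon factor has the same outcome. With no method written down, the remedy would be chosen after the data are seen.

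The second is missing titres. Someone who receives a dose but has no Visit 3 result belongs to the all-dosed population. If the logic of the response ratio (all immunized in the denominator) were carried into the model, that person would be coded as a biological non-responder. This would pull real odds ratios towards 1 and could make a factor linked to dropout look like a risk factor. Section 8.5 says "The Principal Investigator (PI) may discontinue or withdraw a subject from the study for the following reasons at her discretion", and pregnancy heads the list, which would link missingness to sex and age.

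At stake are the risk-factor conclusions of a secondary objective. The primary proportion does not depend on the model.

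**Working it through.** **1. Expected non-responders.** The plan states no sample-size calculation to reproduce, so the count comes from section 5.1.

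- 101 × (1 − 0.70) = 30.3. At the cap, 130 × 0.30 = 39.
- Coefficients: 5 if smoking is one indicator, 6 if the three levels on the data collection form (18.1) are kept, with age linear.
- Per coefficient at 101: 30.3/5 = 6.06 and 30.3/6 = 5.05. At 130: 39/5 = 7.8 and 39/6 = 6.5.
- If response were 80% or 60% at 101: 20.2 or 40.4 non-responders.

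The data are thin, as feared.

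**2. How often ordinary logistic regression would fail.** The documents give no factor prevalences, so this is illustrative. Simulation assumptions: N = 101, 70% response, age uniform from 25 to 65, minority sex 25%, current smoking 10%, past smoking 20%. Diabetes and immunosuppression were each set at the prevalence shown. The ranges run over different true effects.

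| Prevalence of each condition | Trials with no usable estimate for at least one factor |
|---|---|
| 5% | 30–44% |
| 10% | 5–13% |
| 15% | about 2–7% |
| 20% | about 3–5% |

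The result depends almost wholly on an unknown prevalence. When failure does occur it is plain in the output, as a huge or infinite estimate or an empty cell.

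**3. What a prespecified Firth fit would gain.** With true odds ratios of 2 (log 0.693) and 10% prevalence, the mean age coefficient was 0.758 by ordinary logistic regression and 0.690 by Firth.

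- exp(0.758) = 2.13 and exp(0.690) = 1.99.
- Bias relative to root mean squared error: (0.758 − 0.693)/0.477 = 0.14.
- Root mean squared error falls from 0.477 to 0.428, about 10%.
- The median Firth 95% interval for diabetes still spans about 17-fold at 10% prevalence and 55-fold at 5%.

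Precision is the binding limit. For 80% power at two-sided 0.05 with 30% non-response overall, a factor present in half the cohort needs about 43% against 17% non-response: (0.43/0.57)/(0.17/0.83) = 3.7. One present in 10% needs about 69% against 25.7%: (0.69/0.31)/(0.257/0.743), an odds ratio of about 6.4. Choosing the fitting method does not change that.

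**4. Missing titres, if they were coded as non-response.** The documents give no missingness rate, so d is assumed.

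- Share of coded non-responders who are only missing = d/(d + 0.30(1 − d)). This is 15% at d = 5%, 27% at 10% and 37% at 15%.
- Coded non-response = d + (1 − d)p. Take p = 0.30 in the reference group and a true odds ratio of 2, so p = 0.4615 in the exposed group. At d = 10%: 0.370 and 0.515, odds ratio 1.81. At d = 5%: 0.335 and 0.488, odds ratio 1.90.
- A factor with no effect and 20% against 10% missing: 0.44 and 0.37, odds ratio 1.34. In the full simulated model this rejected the null in 9% of trials.
- The same factor with 10% against 5% missing: 0.370 and 0.335, odds ratio 1.17. With 7% against 5%: 0.349 and 0.335, odds ratio 1.06.

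**5. Does the plan call for that coding?** The all-immunized denominator is attached to the reported ratio. The model sentence in 3.1, and those in 13.1 and 13.4, set no outcome class for a missing titre. On the form the result is a blank field, and section 12.1.1 requires missing data to be explained. Regression software drops a blank outcome by default, so counting it as non-response would take a deliberate recode. The two-dose per-protocol analysis in 13.3, read with the completion definition in 7.2, is close to the measured-titre population one would ask for.

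**The case for a change.** The case for a change is respectable. The model serves a listed secondary objective, and nothing labels it exploratory. The objective lists the five factors as examples, and race, ethnicity, department and location are also collected, so a developed model could grow after the data are seen. The synopsis does not say whether response means after one dose or two, and section 13.1 repeats the two-dose endpoint under the secondary heading, where 3.1 and 6.0 have the single-dose one. Per-protocol is not defined. An analyst who meets separation picks the remedy afterwards, and miscoded missing titres would raise no software warning. A few sentences in 13.4 would settle all this at almost no cost.

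What stands is that these details are unwritten and that a sentence or two would be tidy. What does not stand is the step from unwritten to harmful. The plan states no poor method for Firth to replace. No rule turns a missing titre into non-response in the model. The differential dropout is conjecture: section 8.1 excludes women who are pregnant or planning pregnancy, participation lasts about 8 weeks, withdrawal is discretionary, and section 8.4 plans five contact attempts (three emails, two calls) after a missed visit. A place at the head of a list says nothing about frequency.

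**Conclusion.** No change follows. This is a gap that analysts fill sensibly. A binary outcome with five named covariates leads to logistic regression on participants with a measured titre, and any sparse-data failure would show in the output.

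The counts behind the concern are right: 30.3 non-responders at 101, about 5 to 6 per coefficient, and at most 7.8 at the cap of 130. They assume that all 101 enrol, have a titre and respond at 70%. Beyond the counts, every harmful figure rests on prevalences or missingness rates that the documents do not give. Under those assumptions, naming Firth in advance corrects an odds ratio of about 2.13 to about 1.99 and leaves intervals far too wide to settle a risk factor. Missing-as-non-response would attenuate an odds ratio of 2 to 1.90 or 1.81 at 5% or 10% missing, but the plan does not prescribe that coding.

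The study is single-arm and descriptive, with no alpha or power claim, and its primary proportion is the same whatever is done with the model. Readers should treat the risk-factor results as exploratory because of the sample size.

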3.2 Schematic of Study Design

Prior to Enrollment

Up to 130 healthcare workers who have received at least 5 doses of hepatitis B vaccine with aluminum adjuvant and antiHBs <10 MIU/ml
Eligible individuals will be invited to participate by Employee Health Services (EHS) personnel.

Visit 1
Time Point

Obtain written informed consent. Perform baseline assessments and vaccine screening.
Administer hepB-CpG by intramuscular injection

Visit 2
Time Point

Draw blood for antiHBs
Perform baseline assessments and vaccine screening.
Administer hepB-CpG by intramuscular injection

Visit 3
Time Point

Draw blood for antiHBs
Dismiss from study

Final Assessments
EHS personnel will contact participant with antiHBs results

5.0 INTRODUCTION

5.1 Disease Background

Although the recombinant hepatitis B (hepB) vaccine with aluminum adjuvant as a three dose series induces seroprotection in about 95% of individuals, a small number of healthy individuals fail to mount an immune response. Increasing age is an important risk factor for hepB vaccine response.¹ Healthcare personnel are among the individuals for whom protection from hepatitis B infection is very important. Employee Health Service (EHS) at the University of Wisconsin Hospital and Clinics screens employees with documented history of completion of the hepB vaccine 3-dose series for antibody to the hepatitis B surface antigen (anti-HBs) at time of hire. Those who are found to have anti-HBs less than 10 mIU/ml receive a challenge dose.² If the anti-HBs remains less than 10 mIU/ml, two more doses of vaccine are administered. Among the 15,000 employees, about 100 individuals have completed two hepB vaccine with aluminum adjuvant series but remain vaccine non-responders. Heplisav-B (hepB-CpG) is a recently licensed hepB vaccine with a new adjuvant that is more immunogenic in the general adult population and patients with chronic kidney disease or diabetes.³⁻⁵ Given the superior immunogenicity of hepB-CpG in these individuals who were difficult to induce seroprotection, we hypothesize that 70% of the 101 non-responders will mount an immune response to two doses of hepB-CpG.

5.2 Current Standard of Care

With the recent licensure of hepatitis B vaccine with CpG antigen, the Advisory Committee on Immunization Practices (ACIP) has recommended this vaccine series as a vaccine that can be used for adults for whom hepatitis B immunization is recommended. This vaccine series is more immunogenic in the general adult population and patients with chronic kidney disease or diabetes. The ACIP has listed hepB-CpG as a vaccine that can be used for revaccination.

5.3 Investigational Treatment

Although reimmunization is recommended for individuals at high risk of bloodborne pathogen exposure, including healthcare workers, we are prospectively using hepB-CpG series and measuring the vaccine response. Each healthcare worker who wishes to receive the hepB-CpG series on a 0 and 1 month schedule will be asked for written informed consent and will have blood drawn for antiHBs one month after dose 1 and prior to administration of dose 2 and one month after the second dose.

5.4 Rationale

The response rate to hepB-CpG series in healthcare workers who failed to respond to at least 5 doses of hepatitis B vaccine with aluminum adjuvant is not known. If healthcare workers respond to this vaccine series, it may become the standard of care rather than an option among all hepatitis B vaccine preparations.

6.0 STUDY OBJECTIVES AND ENDPOINTS

Objectives	Endpoints
Primary To measure the number of healthcare workers who failed to respond to 5 or more doses of hepatitis B vaccine with aluminum adjuvant who will respond to hepatitis B vaccine with CpG adjuvant series	antiHBs > 10mIU/ml after completion of the series
Secondary To measure the number of healthcare workers who respond to a single dose of hepB-CpG	antiHBs > 10mIU/ml after one dose of hepB-CpG
To determine risk factors associated with hepatitis B vaccine nonresponse, including age, smoking status, sex, diabetes, immunosuppression	Proportion of participants who are nonresponders with each risk factor and develop a multivariate model

7.0 STUDY DESIGN

7.1 General Design

This Phase 4 single center, open label study will measure the response rate to hepB-CpG series in healthcare workers who have received at least 5 doses of hepatitis B vaccine with aluminum adjuvant and have antiHBs < 10mIU/ml.

The study population will consist of 130 healthcare workers who have received at least 5 doses of hepatitis B vaccine with aluminum adjuvant and have antiHBs < 10mIU/ml.

All study visits will be done at Employee Health Services. During visit 1, written informed consent for participation will be obtained. Each participant will be screened for vaccine contraindications. Participants

will be briefly interviewed for known hepatitis B vaccine nonresponse risk factors—age, sex, smoking status, diabetes, and immunosuppression.

Each participant will receive hepB-CpG intramuscularly at visit 1 and at visit 2 will have a blood draw for antiHBs and receive hepB-CpG dose 2 intramuscularly. A blood draw for antiHBs will be done at visit 3 one month following dose 2. The vaccine administration will be documented in the Wisconsin Immunization Registry (the WIR) and the antiHBs results will be retained in the Employee Health electronic medical record (Agility).

Subject accrual will occur over 6 months at UWHealth Employee Health Services. Subjects will complete 3 study visits over the course of approximately 8 weeks. Each subject will contribute 2.

7.2 End of Study Definition

A subject is considered to have completed the study if they receive both doses of hepB-CpG and the blood draw one month after the second dose.

8.0 SUBJECT SELECTION

8.1 Inclusion & Exclusion Criteria

Eligibility will be determined by inclusion and exclusion criteria below.

Inclusion Criteria

1. Willing to provide informed consent.
2. Willing to comply with all study procedures and be available for the duration of the study.
3. healthcare workers who have received at least 5 doses of hepatitis B vaccine with aluminum adjuvant and have antiHBs < 10mIU/ml
4. Individuals at least 18 years of age.
5. Females of childbearing potential will be asked about the possibility of pregnancy as is the standard of care for immunization services. If a female indicates that she may be pregnant, study participation will be postponed until pregnancy is completed or the female reports that she is not pregnant.

Exclusion Criteria

1. Women who are pregnant or planning on becoming pregnant during the study.
2. Allergy to the vaccine or a component of the vaccine
3. Not suitable for study participation due to other reasons, such as inability or unwillingness to comply with the study procedures, at the discretion of the investigators.

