8.2 Subject Identification

8.2.1 Electronic Medical Record (EMR) Query

Potential subjects will be identified via Agility (the EMR used by EHS) query. Eligible individuals are flagged in the system as they require special prophylaxis following bloodborne pathogen exposures. The research team will conduct further prescreening of individual records to further refine the list of potential subjects.

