10.2.3 Enrollment

A research subject will be defined as “enrolled” in the study when they meet the following criteria:

- The subject has been consented by study staff.
- The subject and study staff have completed all screening documentation.
- The study staff has verified that the subject meets all of the inclusion criteria.
- The study staff has verified that subject meets none of the exclusion criteria.
- The subject has been assigned to the protocol by study staff.
- The subject has scheduled a study visit which can follow the informed consent process described above.

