16.2 Feasibility of Recruiting the Required Number of Subjects

Employee Health Services has responsibility for the occupational health and safety of the over 15,000 UWHealth employees. The staff estimates that about 100 individuals will qualify for this study.

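### Could a worker enter on an antiHBs result that predates the last aluminum-adjuvant dose, and so be counted wrongly as a hepB-CpG responder?

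*Combined protocol and SAP*

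**What the plan says.** Section 8.1, criterion 3, admits "healthcare workers who have received at least 5 doses of hepatitis B vaccine with aluminum adjuvant and have antiHBs < 10mIU/ml". It gives no timing for the titre relative to the last dose.

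Section 5.1 describes how the pool arises. Employees with a documented three-dose series are tested at hire, and those below 10 mIU/ml get a challenge dose. Then: "If the anti-HBs remains less than 10 mIU/ml, two more doses of vaccine are administered". The section concludes that "about 100 individuals have completed two hepB vaccine with aluminum adjuvant series but remain vaccine non-responders", and it hypothesizes a 70% response among 101 nonresponders.

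The form in 18.1 lists antiHBs date and result fields after doses 3, 4 and 6. Sections 5.3 and 10.1 place the study blood draws after each hepB-CpG dose and none before the first.

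The synopsis (3.1) describes the people to be invited as those who have "completed at least 5 doses hepB vaccine with aluminum adjuvant series but is anti-HBs negative", and for the analysis it will "report a ratio with the total number immunized as the denominator". On selection, section 8.2.1 says that eligible workers already carry a flag in the employee health record, and adds: "The research team will conduct further prescreening of individual records to further refine the list of potential subjects". Section 10.2.3 makes it a condition of enrollment that "The study staff has verified that the subject meets all of the inclusion criteria".

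**The concern.** The entry threshold is five doses, but the local route to nonresponder status runs to six, and neither the route nor the form marks out a titre between doses 5 and 6. A worker who stopped at five doses, with a last titre taken after dose 4, has at least five doses and a result below 10 mIU/ml on file. Nothing shows that this worker failed the fifth dose.

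The design would not expose such a case. The study has one arm, an absolute antiHBs threshold and no titre immediately before hepB-CpG. Anyone already above 10 mIU/ml because of the last aluminum-adjuvant dose would be counted as responding to hepB-CpG. The error runs in one direction, upward. It would touch both the two-dose primary endpoint and the single-dose secondary endpoint, and the published rate would no longer describe proven nonresponders alone. Staff verify against 8.1, and 8.1 does not state the timing rule.

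**Working it through.** The plan states no figure that depends on this point, so the check has two parts: what the text implies, and how large the effect could be.

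**Text**

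1. Doses on the 5.1 route: 3 (series) + 1 (challenge) + 2 = 6. The threshold in 8.1 is a minimum of 5, so a six-dose worker satisfies it. The two statements do not conflict.
2. Titres on the 5.1 route: stated after the three-dose series and after the challenge dose. A titre after dose 6 is only implied, because these workers are said to remain nonresponders. The form makes it explicit.
3. The same implication covers a five-dose worker. Someone described as a nonresponder after five doses must have had a titre after the fifth. The form can hold it: dose 6 is left blank and the last pre-study antiHBs field is used.
4. Criterion 3 puts the titre in the present tense, after the doses already received. The primary objective (3.1 and 6.0) and 13.2 speak of failure to respond to five or more doses. All point to a titre after the last dose.
5. Section 16.2 states: "The staff estimates that about 100 individuals will qualify for this study". That matches the approximate size of the two-series pool in 5.1, which leaves little visible room for a separate five-dose group. The two figures are approximate, so they do not prove that the group is empty.

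**Size**

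Inputs: n = 101 and p = 70% from 5.1. Three inputs are assumptions, since the documents give no value: the number k of workers without a titre after the last dose (5 or 10), the share r of them above threshold at Visit 1 because of that dose (25% to 50%), and a lower true hepB-CpG response of 50% as an alternative to 70%.

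- Ceiling: one such worker adds at most one responder, 1/101 = 0.99 percentage points.
- Expected extra responders per such worker = r(1 − p), because only someone who would not have responded to hepB-CpG changes the count.

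| r | p | r(1 − p) | k = 5, points of 101 | k = 10, points of 101 |
|---|---|---|---|---|
| 25% | 70% | 0.075 | 0.37 | 0.74 |
| 25% | 50% | 0.125 | 0.62 | 1.24 |
| 50% | 70% | 0.150 | 0.74 | 1.49 |
| 50% | 50% | 0.250 | 1.24 | 2.48 |

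For comparison, 70% of 101 is 70.7, or 71 responders. The exact (Clopper-Pearson) 95% interval for 71/101 is 60.4% to 79.0%, a width of 18.6 points.

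A second view takes s as the share of all participants already above threshold, so that the observed rate is p(1 − s) + s. With p = 70%, s = 5% gives 71.5%, s = 10% gives 73.0% and s = 20% gives 76.0%. The 95% half-width at n = 101 is 1.96 × √(0.70 × 0.30/101) = 8.9 points. The bias 0.30s reaches that size only when s = 8.9/30, about 30%. With k = 10 and r = 50%, s is 5/101, about 5%.

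**The case for a change.** The strongest case for a change is that the eligibility text is looser than the stated population and that tightening it costs almost nothing. Section 10.2.3 has staff verify the inclusion criteria, so a rule absent from 8.1 is not formally among the things verified. The flag and prescreen in 8.2.1 carry no stated titre-date rule either. A six-dose worker whose last recorded titre followed dose 4 would also pass on the literal words. Without a pre-dose titre the study cannot detect such a case, and for the single-dose endpoint the inflation r(1 − p) would be larger if single-dose response is lower than two-dose response. One sentence in 8.1 and a reported count would settle the matter without new data.

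The wording gap stands, and so does the direction of any error. What does not stand is the step from a missing clause to a wrong result. That step needs staff to treat a titre superseded by a later dose as current status, in workers already flagged because they need special prophylaxis after exposure, and against the stated objective. The further request to reconcile five doses with six falls away, because a minimum of five includes six. Nor is it a fault that the per-protocol analysis in 13.3 ignores historical titre dates: it is defined by hepB-CpG doses received.

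**Conclusion.** No change to the plan is needed. Section 8.1 leaves unsaid that the qualifying titre follows the last aluminum-adjuvant dose, but the rest of the protocol makes this plain and staff would apply it in practice. The effect is zero if every participant has a result below 10 mIU/ml after the last such dose, which is what 5.1 and 13.2 describe. The illustrated rise of 0.4 to 2.5 points rests on assumed values of k and r, and at its upper end also on a response rate below the 70% that the protocol hypothesizes. Even then it is small beside the 18.6-point interval. Because the form records the dates of doses and titres, the authors can check the order for every participant and report the number, if any, without a titre after the last pre-study dose. Aligning 8.1 with the wording of 13.2 would be an editorial improvement. It would not alter the sample, the procedures or the primary analysis.

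This conclusion assumes that the existing flag reflects nonresponse after the last dose given. The documents imply this but do not state it. If the recorded dates showed a substantial share of participants without such a titre, the question would need to be reopened.
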